EBIRE: Phase I Study of High Fluence LED-Red Light in Fitzpatrick Skin Types I to III

VA File Number: 18-01-00804

Funding Agency: EBIRE

Principal Investigator: [name], MS

January 12, 2018

Abstract

Objective: To determine the safety of high fluence light emitting diode-red light (HF-LED-RL) phototherapy in Fitzpatrick skin types I to III.

Research Design: This study will be a single-blind, dose-escalation, randomized controlled, Phase 1 study of HF-LED-RL in Fitzpatrick skin types I to III. Subjects with Caucasian or white skin color (Fitzpatrick skin types I, II, or III) will be enrolled sequentially in groups of five (three subjects randomized to HF-LED-RL phototherapy and two subjects randomized to mock therapy). This study is based on the results of the previous “Phase 1 study of LED-RL in Human Skin” (VA file number: 15-12-00756), which demonstrated that HF-LED-RL doses up to 320 J/cm² was safe in all skin types. One male subject with Fitzpatrick skin type V had an adverse event of a blister with HF-LED-RL at fluence of 480 J/cm². The other two subjects, who were of Fitzpatrick skin types I to III, treated with HF-LED-RL at fluence of 480 J/cm² had no adverse event. Therefore, we wanted to explore the safety of HF-LED-RL at doses of 480 J/cm² and 640 J/cm² in Fitzpatrick skin types I to III.

The initial group will receive doses of 480 J/cm² of HF-LED-RL or mock therapy at the Sacramento VA Medical Center Dermatology Clinic three times a week for three consecutive weeks, which is a standard phototherapy regimen based on phototherapy guidelines. An additional group (Group 2: 640 J/cm²) will be sequentially enrolled to receive a higher dose of HF-LED-RL phototherapy or mock therapy. If there is a single adverse event in either Group 1 or Group 2, we will repeat that same dose in a new cohort of five additional subjects (Group 1A or 2A, respectively). This is to account for a

possible outlier effect. The maximally tolerated dose (MTD) will be defined as the dose level below the dose producing unacceptable but reversible adverse toxicity in two or more subjects. After either a MTD has been established or the endpoint dose of 640 J/cm² has been achieved, an additional 27 HF-LED-RL phototherapy subjects (for a total of 30 or 33) and 18 mock therapy subjects (for a total of 20 or 22), determined randomly, will be enrolled for a total of 50 subjects, such that it can be concluded with 95% confidence that fewer than 1 person in 10 will experience an adverse event.

Methods: Healthy subjects, any sex, ethnicity, and age with Fitzpatrick skin types I to III that do not meet exclusion criteria and whose nondominant proximal anterior forearm is wide enough to ensure reproducible placement of HF-LED-RL phototherapy or mock therapy hand-held unit will be recruited. Subjects with light-sensitive conditions or on photosensitizing medications, subjects with open wounds, diabetes, fibrotic skin diseases or other skin conditions affecting the nondominant proximal anterior forearm will be excluded from the study. Subjects with tattoos that cover the procedure site will also be excluded, as the tattoos may affect study findings due to altered light penetration or reflection. Subjects with Fitzpatrick skin types IV, V, and VI (darker skin phenotypes) and subjects who have participated in the "Phase 1 Study of LED-RL in Human Skin" (VA file number #15-12-00756) at the Sacramento VA Medical Center will be excluded.

Clinical Significance: The effects of visible light, while common in our environment (visible spectrum accounts for 44% of total solar energy), remain undefined. An important safety feature of visible red light (600 nm to 700 nm) is that it does not generate pro-carcinogenic DNA damage as does ultraviolet (UV) light. Recently

published clinical observations indicate that red light in combination with other modalities, such as photosensitizers in combined red light photodynamic therapy, can treat skin disease. However, preliminary in vitro data generated by our research group suggests that red light can function as a stand-alone treatment, eliminating the side-effects of chemical photosensitizers and the potential long-term harm of current UV phototherapy. Furthermore, commercially available light emitting diode-red light (LED-RL) units exist and are already FDA-cleared for other dermatological uses (such as rhytides and acne), thus clinical translation for use in skin diseases could occur relatively quickly following safety and efficacy demonstration. Currently, limited data exists pertaining to HF-LED-RL safety in different Fitzpatrick skin types. The uniqueness and importance of our study for medical science is that this will be the first clinical study of HF-LED-RL to evaluate the safety and regimen of these doses (480 and 640 J/cm²) in Fitzpatrick skin types I to III. Evaluating safety of HF-LED-RL phototherapy is important as HF-LED-RL may have the potential to treat skin diseases. To our knowledge, no clinical trials have been performed to determine the safety of HF-LED-RL in Fitzpatrick skin types I to III. Therefore, the innovation of this approach is that we intend to study the safety of HF-LED-RL modality in Fitzpatrick skin types I to III.

List of Abbreviations

HF-LED-RL, high fluence light-emitting diode-red light

MRSD, maximum recommended starting dose

MTD, maximum tolerated dose

UV, ultraviolet

Definitions

Fitzpatrick Skin Types: A method to categorize a person's skin based on his/her skin's reaction to sun or ultraviolet light exposure (Table 1). (Fitzpatrick 1988) It ranges from type I (always burn, never tan) to type VI (never burn, always tan). In general, Caucasian or white skin color is considered Fitzpatrick skin types I, II, and III, while darker skin colors are considered Fitzpatrick skin types IV, V, and VI.

Table 1. Skin type and sunburn sensitivity (Fitzpatrick Classification) (Fitzpatrick 1988)

Fitzpatrick Skin Type	Response to Sun Exposure	Basic Skin Color
I	Always sunburns, never tans	Pale white
II	Sunburns easily, develops a light Tan	White
III	Sunburns moderately, develops a moderate tan	White
IV	Sunburns minimally to rarely, develops a deep tan	Light brown/olive
V	Never sunburns, develops a dark tan	Brown

2.0 Introduction

- The effects of visible light, while common in our environment (visible spectrum accounts for 44% of total solar energy), remain undefined. An important safety feature of visible red light (600 nm to 700 nm) is that it does not generate pro-carcinogenic DNA damage as does ultraviolet (UV) light. Recently published clinical observations indicate that red light in combination with other modalities such as photosensitizers in combined red light photodynamic therapy can treat skin diseases. However, preliminary in vitro data generated by our research group suggests that red light can function as a stand-alone treatment, eliminating the side-effects of chemical photosensitizers and the potential long-term harm of current UV therapy. Furthermore, commercially available light emitting diode-red light (LED-RL) units exist and are already FDA-cleared for other dermatological uses (such as rhytides and acne), thus clinical translation for use in skin diseases could occur relatively quickly following safety and efficacy demonstration.
- We do not classify erythema (redness) lasting less than 24 hours as an adverse event in our study. Erythema is a common expected outcome that

may occur in at least 10% of subjects as previously demonstrated in published studies.(Sadick 2008, Sadick 2008) Common expected procedure outcomes include: warmth, erythema (redness), and edema (swelling) that is expected to last less than 24 hours. To our knowledge, there are no animal studies that have utilized this device (Omnilux new-U) at these doses (480 and 640 J/cm²). This device has a FDA 510K clearance, is sold for home use, and is generally regarded as safe in humans.

- In a randomized, controlled, dose escalation Phase I study of LED-RL in Human Skin (VA file 15-12-00756) conducted by our research group (hereinafter referred to as “previous Phase 1 LED-RL study”), we studied HF-LED-RL at doses of 160 J/cm², 320 J/cm², and 480 J/cm² in all Fitzpatrick skin types. The maximum recommended starting dose (MRSD) of 160 J/cm² is based upon previously published maximum doses of LED-RL phototherapy used in clinical studies that demonstrated clinical safety with no adverse events. (Sadick 2008, Sadick 2008). In the “previous Phase 1 LED-RL study”, the MRSD (160 J/cm²) was administered to Group 1 and the dose was escalated in subsequent groups using the classical method for dose escalation as described by Spilker: starting with dose (X) increased by an equal amount (in this instance: X=160 J/cm², 2X=320 J/cm², 3X=480 J/cm², 4X=640 J/cm²). We demonstrated that the maximum tolerated dose (MTD) for HF-LED-RL was 320 J/cm² in the “previous Phase 1 LED-RL study” based on an adverse event of a blister in one male subject with Fitzpatrick skin type V with HF-LED-RL at fluence of 480 J/cm² (unpublished

data). The other two subjects, who were of Fitzpatrick skin types I to III, treated with HF-LED-RL at fluence of 480 J/cm² had no adverse event.

48 subjects had no response or adverse event to any dose of HF-LED-RL or mock therapy. Eleven subjects had an expected, anticipated adverse event: One subject had faint erythema/redness that resolved after approximately one day (less than 48 hours) and ten subjects had transient post-inflammatory hyperpigmentation (PIH), which is mild tanning.

- Currently, limited data exists pertaining to HF-LED-RL safety in different Fitzpatrick skin types. Fitzpatrick skin types is a method to categorize skin types based on their reaction to sun or ultraviolet light exposure.(Fitzpatrick 1988) It ranges from type I (always burn, never tan) to type VI (never burn, always tan). In general, Caucasian (white) skin types are considered Fitzpatrick skin types I, II, or III while darker skin types are considered Fitzpatrick skin types IV, V, or VI. In the “previous Phase 1 LED-RL Study”, we did not evaluate or record Fitzpatrick skin types, but we recorded data for race and ethnicity based on National Institutes of Health (NIH) guidelines. Ethnicity and race corresponds closely with Fitzpatrick skin types as Caucasian skin types are Fitzpatrick skin types I to III and ethnic people are Fitzpatrick skin types IV to VI. Therefore, Fitzpatrick skin types scoring of subjects listed in ‘Part 1’ was based on race and ethnicity.
- We demonstrated in the “previous Phase 1 LED-RL study” that darker skin phenotypes (Fitzpatrick skin types IV, V, and VI) are more photosensitive to visible red light, as evident by an adverse event of a blister in one study

subject with Fitzpatrick skin type V at 480 J/cm² HF-LED-RL. The other two subjects, who were of Fitzpatrick skin types I to III, treated with HF-LED-RL at fluence of 480 J/cm² had no adverse event. Therefore, we wanted to explore the safety of HF-LED-RL at doses of 480 J/cm² and 640 J/cm² in Fitzpatrick skin types I to III. This finding that skin of color subjects may be more photosensitive to HF-LED-RL than Caucasian subjects is significant to the scientific community because we demonstrated that Fitzpatrick skin types respond to visible red light differently than to ultraviolet light. Darker skin (Fitzpatrick skin types IV to VI) is photoprotective for ultraviolet wavelengths, but more photosensitive to HF-LED-RL than subjects with light skin (Fitzpatrick skin types I to III). This photosensitivity may be due to increased skin pigment melanin which absorbs visible light. This hypothesis is supported by and corresponds to clinical observations with the use of visible light laser therapy in patients with skin of color. Therefore, this study will investigate the differential effects of HF-LED-RL on Fitzpatrick skin types I to III.

- This Phase 1 study (Storer 1989 – Phase 1 study design) will establish the safety of HF-LED-RL up to 640 J/cm² in human skin in this population of Fitzpatrick skin types I, II, and III. The results of this phase I study may establish differential safety of HF-LED-RL in Fitzpatrick skin types, which would determine dose stratification and treatment parameters for future clinical studies that use HF-LED-RL as a therapeutic modality. It may also determine what dose of HF-LED-RL is safe to use in Fitzpatrick skin types I

to III. Upon successful demonstration of safety of HF-LED-RL in Fitzpatrick skin types I to III, future phase II studies may reference our phase I safety data to perform efficacy studies of HF-LED-RL in human skin for treatment of skin diseases. The uniqueness and importance of our study for medical science is that this will be the first study of HF-LED-RL in humans with Fitzpatrick skin types I to III to evaluate the safety and regimen of these doses (480 and 640 J/cm²). Evaluating safety of HF-LED-RL phototherapy is important as HF-LED-RL may have the potential to treat skin diseases. To our knowledge, no clinical trials have been performed to determine the safety of HF-LED-RL in Fitzpatrick skin types I to III. Therefore, the innovation of this approach is that we intend to study the safety of HF-LED-RL modality in Fitzpatrick skin types I to III.

- This randomized, controlled Phase 1 clinical study requires a study temperature-matched control, which is the mock therapy device. The mock therapy will serve as a control and help evaluate if side effects are due to HF-LED-RL light or the heat output that is emitted from the study device. If an adverse event occurs with the HF-LED-RL device only, then the HF-LED-RL light may have caused the adverse event. If an adverse event occurs with the mock device only, then the adverse event may have been caused by the heat output. However, if the same adverse event occurs with both HF-LED-RL and mock therapy at the same time duration, then the adverse event may have been caused by the heat output generated from both HF-LED-RL and mock devices.

- Potential subjects who are willing and eligible for the study will be recruited from the Sacramento VA Medical Center, Mather. No vulnerable populations will be recruited to this study. Subjects with Fitzpatrick skin types IV, V, and VI will be excluded because the MTD for subjects with Fitzpatrick skin types IV, V, and VI was established in the “previous Phase 1 LED-RL study” as 320 J/cm² HF-LED-RL due to an adverse event of a blister in one study subject with Fitzpatrick skin type V at 480 J/cm² HF-LED-RL. No subsequent testing of 480 J/cm² was performed in subjects with Fitzpatrick skin types IV, V, and VI due to the study design of the “previous Phase 1 LED-RL study” where if any adverse event occurred, further testing at that dose would be discontinued. In this study, we will not test higher fluences of 480 J/cm² and 640 J/cm² in subjects with Fitzpatrick skin types IV, V, and VI. Subjects who have previously participated in the “previous Phase 1 LED-RL study” will be excluded to maintain unbiased results.

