5.0 Study Procedures

5.1 Study Design

- This is a single-blind, randomized, ascending dose escalation Phase I study of HF-LED-RL in healthy subjects with Fitzpatrick skin types I to III to evaluate safety of HF-LED-RL in Fitzpatrick skin types I to III (Figure 1). The study endpoint of 640 J/cm² is due to feasibility, as this dose corresponds to two hours of HF-LED-RL irradiation, and we anticipate decreased subject compliance with HF-LED-RL exposures longer than 2 hours in duration. The study endpoint of 640 J/cm² was also selected as this dose demonstrated increased anti-fibrotic properties in vitro compared to lower doses of HF-LED-RL (Mamalis 2015). Subjects will receive HF-LED-RL phototherapy or mock therapy three times a week for

three consecutive weeks, which is a standard phototherapy regimen based on phototherapy guidelines (Anderson et al 2015, Menter et al 2010, Zanolli et al 2004).

The HF-LED-RL light source is a commercially available Omnilux New-U hand-held LED-RL phototherapy unit (provided by Photo Therapeutics, Carlsbad, CA, USA), and is FDA-cleared for treatment of periorbital rhytides (crow's feet) with doses up to 160 J/cm². The temperature-matched mock therapy unit, also provided by Photo Therapeutics, Carlsbad, CA, USA, generates only heat output comparable to heat generated by the HF-LED-RL device, which is less than two degrees Celsius of heat output, and does not emit HF-LED-RL.

We do not classify erythema (redness) lasting less than 24 hours as an adverse event in our study, and is expected to occur in at least 10% of subjects as previously demonstrated in published studies (Sadick 2008, Sadick 2008). Common expected procedure outcomes include: warmth, erythema (redness), and edema (swelling) that is expected to last less than 24 hours.

- The maximum tolerated dose (MTD) is defined as the dose level below the dose producing unacceptable but reversible toxicity in two or more subjects ($\geq 20\%$) and is considered the upper limit of subject tolerance. If two or more subjects experiences any adverse event (including: first-degree or higher skin burning or blistering, erythema lasting more than 24 hours, swelling, pain, ulceration, infection, change in sensation, and/or

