After either a MTD has been established or the study endpoint of 640 J/cm2 has been achieved, an additional 27 HF-LED-RL phototherapy subjects (for a total of 30 or 33) and 18 mock therapy (for a total of 20 or 22) (determined randomly) will be enrolled to satisfy Hanley's Rule of Three, such that it can be concluded with 95% confidence that fewer than 1 person in 10 will experience an adverse event (Figure 3). (Hanley 1983) If the MTD is 320 J/cm2, then the study will be stopped and no further testing of the MTD of 320 J/cm2 in the larger cohort will be indicated because the MTD of 320 J/cm2 was already tested in a large cohort in the "previous Phase 1 LED-RL study". Of the larger expansion cohort, the study will be halted (stopped) if adverse events determined to be device related equals or exceeds 30%.

This clinical trial will be registered on <https://clinicaltrials.gov> following IRB approval and prior to subject enrollment.

- The subject will receive standard of care treatment in the dermatology clinic for any adverse event. Physical examination/visual inspection of the treated forearm will occur at every study visit. Treatment will be initiated, if indicated, for any procedural outcomes or adverse events noted at every study visit. Any general dermatology adverse events will be managed by [name] in the Dermatology clinic, per standard of care. If a skin ulcer occurs, we will record the skin ulceration as a superficial ulceration

(meaning it is nearly flush with the skin) or, if measurable, the depth of ulceration in millimeters. If skin ulceration occurs, we will consult [name], who is an expert in wound healing and head of the Sacramento VA wound clinic, for management. If change in sensation or muscle weakness occurs in a subject, the subject will be sent to Sacramento VA Emergency Room for urgent grading and management. If there are any other adverse events that cannot be managed in the Dermatology clinic, the subject will be sent to the Sacramento VA Emergency Room for urgent care.

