5.6 Data Analysis

- Once all study subjects have finished all study procedures and data collection is complete, [name], [name], and/or [name] will then be performing the data analysis. Data analysis will include analysis of demographics (e.g. age, gender, ethnicity, race, Fitzpatrick skin type) in each cohort by HF-LED-RL or mock therapy dose, frequency of adverse events by HF-LED-RL or mock therapy

groups, mean duration of erythema, total duration of erythema, and subgroup analysis by demographics of adverse events. Self-reported outcomes of erythema duration are based on self-reporting from subject's diary.

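### The stated logic for attributing an adverse event to light or heat goes by presence or absence in each arm and ignores how often the event occurs

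*Combined protocol and SAP*

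**What the plan says.** Section 2.0 gives the purpose of the control: "The mock therapy will serve as a control and help evaluate if side effects are due to HF-LED-RL light or the heat output". Three readings follow.

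- Event on the active device only: "If an adverse event occurs with the HF-LED-RL device only, then the HF-LED-RL light may have caused the adverse event".
- Event on the mock device only: "If an adverse event occurs with the mock device only, then the adverse event may have been caused by the heat output".
- Event in both arms, that is, "if the same adverse event occurs with both HF-LED-RL and mock therapy at the same time duration": heat from both devices is again named as the possible cause.

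None of the three refers to the number of subjects affected in either arm. Section 5.1 describes a mock unit that "generates only heat output comparable to heat generated by the HF-LED-RL device". It sets the final arm sizes at the dose taken into expansion as "an additional 27 HF-LED-RL phototherapy subjects (for a total of 30 or 33") and "18 mock therapy (for a total of 20 or 22"). Section 5.6 lists "frequency of adverse events by HF-LED-RL or mock therapy" groups among its summaries. It names no difference, interval or test, and does not return to the light-versus-heat question.

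**The concern.** The mock arm is there to tell light from heat, and the only stated way of doing so discards the information that a randomised comparison provides. Two errors follow.

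- **Heat read as light.** A heat-only event should have about the same rate in both arms, because the heat is matched. If it is uncommon, it may by chance appear only in the active arm, which is half as large again as the mock arm.
- **Light read as heat.** One occurrence on mock moves the event into the both-arms category, however many more occur on the active device.

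The second error matters more in a study whose objective is safety and whose results are meant to be available to later efficacy studies. A clear excess on the active device could be put down to warmth.

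**Working it through.** **Inputs from the documents.** 30 active and 20 mock subjects (33 and 22 if a cohort is repeated), from Section 5.1; the three readings in Section 2.0; matched heat, from Section 5.1. **Assumed:** event rates, since none is given for this comparison. Each rate is for one event type, because the both-arms reading requires the same event. Subjects are treated as independent.

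**The plan's own figure.** The Rule of Three gives 3/30 = 0.10, and the exact bound for zero events in 30 is 1 − 0.05^(1/30) = 0.095. The stated sample-size claim reproduces. It concerns a single group and gives no basis for comparing arms.

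**Heat alone, same rate p in both arms.** The logic points to light when events occur in the active arm only:

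P = [1 − (1 − p)^30] × (1 − p)^20

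At p = 0.05: (1 − 0.2146) × 0.3585 = 0.282. Dividing by the chance of any event, 1 − 0.95^50 = 0.923, gives 0.305.

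| Rate in both arms | Points to light, all trials | Points to light, trials with any event |
|---|---|---|
| 1% | 21% | 54% |
| 2% | 30% | 48% |
| 5% | 28% | 31% |
| 10% | 12% | 12% |
| 20% | 1% | 1% |

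With 33 versus 22 the all-trials figures are 23%, 31%, 26%, 10% and 1%. If exactly one event occurs among the 50 subjects, it falls in the active arm with probability 30/50 = 60% from allocation alone.

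**Light raises the rate.** The logic points to heat when events occur in both arms:

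P = [1 − (1 − p₁)^30] × [1 − (1 − p₂)^20]

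At p₁ = 0.20 and p₂ = 0.05: 0.9988 × 0.6415 = 0.641.

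| Mock rate | Points to heat, active rate 20% or 30% |
|---|---|
| 1% | 18% |
| 2% | 33% |
| 5% | 64% |
| 10% | 88% |

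The first factor is already close to 1 at an active rate of 20%, so a stronger light effect does not reduce the error. The mock rate alone drives it. In these trials heat does contribute something; what the logic misses is the excess on the active device.

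**Example.** 10/30 versus 1/20 falls under heat. The difference is 33.3% − 5.0% = 28.3 points, Newcombe 95% interval 5 to 47, Fisher two-sided p = 0.033. Conversely, 3/30 versus 0/20 falls under light, yet the interval is −7 to +26 points.

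**What an empty mock arm shows.** Zero events in 20 is compatible with a mock rate up to 1 − 0.05^(1/20) = 13.9% (one-sided 95%). Events on the active device only therefore do not exclude heat.

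**The alternative.** If the statement rests on a Newcombe 95% interval lying above zero, a heat-only event is called light in 0.1%, 0.9% and 1.8% of trials at rates of 5%, 10% and 20%. At 20% versus 5%, the interval lies above zero in about 26% of trials.

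**The case against.** The text is background in the Introduction. It explains why a temperature-matched control is wanted, and every sentence is hedged. The analysis section plans frequencies by arm, so 10/30 versus 1/20 would be visible to any reader. The error percentages describe a deterministic rule that the protocol does not formally adopt, at rates that it does not supply. Low mock rates are plausible: the heat output is under two degrees Celsius, and erythema under 24 hours is not counted as an adverse event. The trial is descriptive and not sized for a between-arm contrast, and the proposed method would leave the cause undetermined in about three of four trials at 20% versus 5%.

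Much of this stands. The hedging means no firm causal conclusion is prescribed, and the percentages apply only to the logic followed as written. Low rates help only in one direction: at 1% light is read as heat in 18% of trials, but heat is read as light in 54% of trials with any event. A frequency table shows the imbalance without saying how to interpret it, and the only interpretive text points the other way.

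A reader might infer three stronger things, and the documents do not support them:

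- **That this is the mock arm's only use.** Section 5.1 also counts mock events in the escalation rule, and Section 5.6 tabulates them.
- **That escalation could be misdirected.** The rule counts events in either arm and does not ask whether light or heat caused them.
- **That the 30% halt could be misapplied.** Section 5.1 does not say how device-relatedness is determined, and Section 2.0 describes the heat as coming from the study device. An event attributed to heat could still be device related.

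**Conclusion.** The concern holds as a matter of interpreting cause. The only stated logic for separating light from heat ignores frequency, and nothing in the analysis section corrects it. How often it misleads depends strongly on the assumed rates. Heat read as light is common at rates of about 5% or less and rare at 20%. Light read as heat occurs in a third or more of trials once the mock rate reaches about 2%. These results assume 30 versus 20 independent subjects, heat equal in both arms, and the logic applied as written. No dose or stopping decision is shown to change, and the Rule of Three sample size is not in question.

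**What to change.** In Sections 2.0 and 5.6, replace the presence/absence logic. For each event type and for any event, report the proportion of subjects affected by arm at the same dose and exposure time, with the risk difference and a Newcombe or exact 95% interval. Base the light-versus-heat statement on that interval, call the cause undetermined when it includes zero, and label the comparison descriptive.

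This uses data already collected and costs a sentence in each section and one table. The downside is wide intervals and fewer firm attributions.
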